8.5.2 Analysis of the secondary variable(s)

For secondary endpoints, continuous variables, e.g. change in peak eos counts, change in blood eosinophil count, change in symptom scores from pre- to post-treatment, and change in endoscopic scores from pre- to post-treatment at each study visit will be analysed and compared in a repeated measure ANOVA model. Proper transformation of data, e.g. logarithmic, or non-parametric methods may be applied to satisfy statistical assumptions. Categorical responses, e.g. response rate will also be compared using a Fisher's exact test.

Safety endpoints, i.e. adverse events (by organ system and preferred terms), SAEs, as well as demographic variables will be summarized by treatment groups. The total numbers of AE's as well as number of patients with an AE will be summarized via N and percentages.

8.5.3 Subgroup analysis (if applicable)

No subgroup analysis is planned, other than a per-protocol analysis of efficacy.

8.5.4 Interim analysis

No interim analysis is planned.

8.5.5 Sensitivity analysis (if applicable)

Logistic regression models will be explored in the primary efficacy endpoint analysis, namely the remission rate. In addition to treatment groups, other terms may be included in the regression model, e.g. gender, age, and baseline eosinophil count, to assess the sensitivity of the primary results.

8.5.6 Exploratory analysis (if applicable))

Additional exploratory analysis may be conducted for the exploratory objective measures.

9. STUDY AND DATA MANAGEMENT

9.1 Training of study site personnel and local providers

All study staff listed on the site delegation log must be trained on the conduct of the study prior before engaging in any study-related activities

Due to COVID-19, drug may be administered by local providers to some patients. Local providers medically trained to administer subcutaneous injections (RNs, MDs, PharmD) will provide the study injections. Local providers will be asked to provide evidence of competency in subcutaneous injections and/or injection certification to the study staff. Local providers must show competency in monitoring for post injection reactions.

9.2 Monitoring of the study

The Principle Investigator will designate a study monitor who will visit the study site prior to enrollment of the first patient, and periodically throughout the study. The monitor will compare CRF entries with the corresponding source documents, as outlined in the ICH guidelines. The study monitor may also review subject ICFs, patient recruitment and follow-up documentation, AEs, SAEs, and concomitant therapy; along with records of dispensation of study drug, compliance, and accountability. A copy of the drug dispensing log must be provided to the sponsor upon request.

9.2.1 Source data

Study staff must prepare and maintain adequate and accurate records of each subject's study participation (i.e. source documents). All source documents must be kept on file with the CRFs. (CRFs may be either paper or electronic [eCRF]). CRFs and source documents must be available at all times for inspection by authorized representatives of the Principle Investigator regulatory agencies.

9.2.2 Study agreements

If the PI chooses to close out the study site (for example, due to lack of subject enrollment within a reasonable period of time, violation of the study agreement, breach of protocol, early attainment of study enrollment targets, etc.), the PI will notify involved individuals in writing.

The appropriate regulatory agencies must be informed according to applicable requirements, and adequate consideration must be given to the protection of the subjects' interests.

9.2.3 Archiving of study documents

All essential study documents must be retained by the investigator for at least 3 years after the conclusion or discontinuation of the trial. Prior to destroying any essential documents, the investigator must consult with the PI. If and when destruction is authorized, records must be destroyed in a manner that ensures confidentiality. If an investigator can no longer ensure

archiving, the sponsor and the investigator will agree upon a suitable designation for transferring the essential records.

9.3 Study timetable and end of study

The end of study will be at a follow up visit at Week 16 ± 3 days. For subjects who are remote, the follow up visit can be performed at a local site, in which vital signs, physical exam, urine pregnancy and lab work will be performed. Results will be released to CCHMC upon authorization of release of medical information/specimen by the subject.

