3.10.3 Early withdrawal

Subjects may be asked to complete an EOT/Early withdrawal visit prior to withdrawal per the discretion of the PI.

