4.3 Follow-up period

Visit 6 (Week 16 Follow-Up)

- Physical Exam, Vital Signs, weight
- Adverse Events
- Pregnancy testing: urine
- Clinical labs (hematology and serum chemistry, urinalysis, IgE)

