6.4.1 Time period for collection of adverse events

Adverse events (including SAEs) will be collected from the time of consent until a subject completes study participation, or until 30 days after he/she prematurely withdraws (without withdrawing consent) or is withdrawn from the study.

Adverse events (including SAEs) may be discovered through any of these methods:

- Observing the participant.
- Interviewing the participant
- Receiving an unsolicited complaint from the participant.

In addition, an abnormal value or result from a clinical or laboratory evaluation can also indicate an adverse event, as defined in Definition of adverse events.

Throughout the study, the investigator will record adverse events and serious adverse events on the appropriate AE/SAE CRF, regardless of the relationship to study therapy regimen or study procedure.

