If deterioration in a laboratory value/vital sign is associated with clinical signs and symptoms, the sign or symptom will be reported as an AE and the associated laboratory result/vital sign will be considered as additional information. Wherever possible the reporting investigator uses the clinical, rather than the laboratory term (eg, anaemia versus low haemoglobin value). In the absence of clinical signs or symptoms, clinically relevant deteriorations in nonmandated parameters should be reported as AE(s).

Any new or aggravated clinically relevant abnormal medical finding at a physical examination as compared with the baseline assessment will be reported as an AE.

Since the most common adverse effects previously noted for Benralizumab has been breathing difficulty, nasopharyngitis, upper respiratory infection, headache, bronchitis, sinusitis, influenza and pharyngitis, surveillance for these events will be undertaken. Any of these events that fulfil the criteria of an AE as judged by the investigator should be reported using the standard procedures for assessing severity, causality and seriousness.

6.5 **Reporting of serious adverse events**

All SAEs have to be reported to AstraZeneca, whether or not considered causally related to benralizumab, or to the study procedure(s). The reporting period for SAEs is the period immediately following the time that written informed consent is obtained through 60 days after the last dose of benralizumab. The investigator is responsible for informing the IRB as per local requirements.

The investigator and other site personnel must inform the FDA, via a MedWatch/AdEERs form, of any serious or unexpected adverse events that occur in accordance with the reporting obligations of 21 CFR 312.32, and will concurrently forward all such reports to AZ. A copy of the MedWatch/AdEERs report must be faxed or email to AstraZeneca at the time the event is reported to the FDA. It is the responsibility of the investigator to compile all necessary information and ensure that the FDA receives a report according to the FDA reporting requirement timelines and to ensure that these reports are also submitted to AstraZeneca at the same time.

When reporting to AstraZeneca, a cover page should accompany the MedWatch/AdEERs form indicating the following:

- Investigator Sponsored Study (ISS)
- The investigator IND number assigned by the FDA
- The investigator's name and address

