6.8 Management of toxicities

The study is designed to administer uniform dose of 30mg of benralizumab. In the event of SAEs, the subject will be discontinued from the study and the event reported as mentioned above. Continued enrolment at reduced dosage is not applicable. **Dose Reductions**: Not applicable.

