7.7 Concomitant and other treatments

Rescue/Supportive Medication/Class of drug:	Usage:
Study participants should continue their baseline medications and dietary therapy. Rescue medicines for EGID exacerbations are not allowed and will lead to study withdrawal.	
During study visits, participants will be allowed to have EMLA or topical analgesic (Pain Ease or Spray & Stretch) for the purpose of venepuncture/IV insertion	

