9.4 Data management

Serious Adverse Event (SAE) Reconciliation

SAEs will be followed until they are resolved, with or without sequlae, or until the end of study participation, or until 30 days after the subject prematurely withdraws from the study (without withdrawing consent)/or is withdrawn from the study, whichever occurs first.

Data Management of genotype data

N/A

Data associated with human biological samples

N/A

Management of external data

N/A

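### SAE collection under Section 6.4.1 can stop before the 60-day period in Section 6.5 closes: up to 30 days early after withdrawal, and nominally 4 days early for completers who skip OLE I

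*Combined protocol and SAP*

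**What the plan says.** Four provisions bear on when SAE capture ends.

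- **Section 6.5** requires every SAE, related or not, to be reported from consent "through 60 days after the last dose of benralizumab".
- **Section 6.4.1** collects adverse events, and names SAEs among them, until the subject completes participation or "until 30 days after he/she prematurely withdraws (without withdrawing consent) or is withdrawn from the study".
- **Section 9.3** gives the end of participation for a subject who takes no extension treatment: "The end of study will be at a follow up visit at Week 16 ± 3 days". Section 4.3 places that follow-up at Visit 6, and a footnote to the study plan table reserves some Visit 5/6 procedures for subjects who do not continue to OLE I.
- **Section 9.4** follows SAEs until resolution, end of participation, "or until 30 days after the subject prematurely withdraws from the study", whichever comes first.

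The early-withdrawal visit is optional and takes place before withdrawal: "Subjects may be asked to complete an EOT/Early withdrawal visit prior to withdrawal per the discretion of the PI". Two sections send subjects out of the study. Section 6.8 says "In the event of SAEs, the subject will be discontinued from the study", and Section 7.7 says "Rescue medicines for EGID exacerbations are not allowed and will lead to study withdrawal". No visit or call is tied to day 60 after the last dose, and nothing says which rule prevails.

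**The concern.** A site can report only the SAEs it learns of. Between the stop in Section 6.4.1 and day 60, the site still has a duty to report but no instruction to ask and no scheduled contact at which to ask. Safety is a stated objective (Section 2.3), and SAEs are to be summarised by treatment group (Section 8.5.2). In a trial of about 26 subjects, a single missed event would change that summary. Subjects who leave early have the shortest coverage, and by Sections 6.8 and 7.7 they include people who leave because of an SAE or a disease flare.

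**Working it through.** The plan gives 60 days as a rule, not as a calculated figure, so there is nothing to reproduce. The check is day arithmetic.

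**Inputs**
- SAE period: 60 days after the last dose (6.5).
- Collection stop after withdrawal: 30 days (6.4.1).
- Double-blind doses at Weeks 0, 4 and 8, so the last is on day 8 × 7 = 56 (3.3, 4.2).
- Last visit without OLE I: Week 16, day 16 × 7 = 112 (4.3, 9.3).
- Windows: ±3 days in 9.3; ±4 days in the study plan table, counted from the previous visit.
- Dropout allowance: 26 enrolled − 24 completed = 2 (8.2).

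**Withdrawn subjects.** For withdrawal x days after the last dose, consent not withdrawn:

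coverage = x + 30 days; shortfall = max(0, 60 − (x + 30)) = max(0, 30 − x).

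- x = 0: collection ends on day 30, 30 days short
- x = 7: day 37, 23 short
- x = 14: day 44, 16 short
- x = 28: day 58, 2 short
- x = 30 or more: none

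Double-blind doses are nominally 28 days apart. A subject withdrawn while dosing is on schedule is therefore at most 28 days from a dose and has a shortfall of at least 2 days.

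**Completers who skip OLE I.**

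- Nominal: 112 − 56 = 56 days; 60 − 56 = 4 days short.
- Dose exactly on day 56 and only the ±3 days of 9.3: 53 to 59 days, so 7 to 1 days short.
- Table windows chained over Visit 4 to 5 and Visit 5 to 6: 56 ± (4 + 4) = 48 to 64 days. The result runs from 60 − 48 = 12 days short to 64 − 60 = 4 days past day 60.

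To reach 60 days after a Week 8 dose, collection must run to day 56 + 60 = 116, which is Week 16 plus 4 days.

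**OLE II completers.** Last scheduled dose at Week 84 and safety visit at Week 96 in the table: (96 − 84) × 7 = 84 days. There is no shortfall.

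**The case against.** The best reply is that Section 6.5 is the SAE-specific provision and already settles the duty, so an SAE that comes to the site's notice on day 50 must be reported whatever Section 6.4.1 says. That is right. A reader might infer that such events would go unreported, and the documents do not support that. What is missing is a rule or contact to find them.

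Section 6.4.2 also keeps unresolved adverse events under follow-up for as long as medically needed. This protects a subject withdrawn with an ongoing SAE as far as that event goes. It covers only events open at the last assessment and does not collect new SAEs, so the gap stays.

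The Week 16 shortfall is small and lies within visit tolerance. A reader might take 1 to 7 days as the shortfall for every subject who skips OLE I. That needs a dose on exactly day 56 and the narrower window of 9.3. Under the table's windows some subjects pass day 60. The nominal 4 days is the safest figure.

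Three other stronger readings also fail:
- Section 9.4 might be read as a second stop on collection. It governs how long SAEs already found are followed; the collection stop is in 6.4.1.
- Sections 6.8 and 7.7 might be read as forcing out every subject with an SAE or any rescue use. Section 3.10 is softer: withdrawal is permitted, not required, and it refers to SAEs related to therapy and to rescue use the investigator judges substantial.
- The 30-day follow-up in Section 3.3 might be applied to the Week 12 endoscopy. That text is damaged in the extract and the start of the period cannot be read, so no figure is drawn from it.

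**Conclusion.** The conflict stands and is minor. Withdrawal soon after a dose is the larger part: up to 30 days of SAE collection lost per subject. At the planned dropout this concerns up to 2 double-blind subjects, and fewer if a dropout withdraws consent or leaves 30 days or more after a dose. Skipping OLE I costs a nominal 4 days. The documents do not say how many subjects will skip OLE I or withdraw during the extensions.

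The rules apply equally to both arms, so a reader who infers a biased treatment comparison goes beyond the text. No gap is claimed for OLE II completers, or for subjects who stop after OLE I, whose follow-up depends on the damaged part of Section 3.3.

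Two assumptions matter. First, the last dose of benralizumab in Section 6.5 is read as the last dose of study drug. Taken literally, it sets no end date for a placebo subject who never enters an extension. Second, dosing follows Section 4.2, with the first dose at Visit 2. Section 7.2 names Visit 3; read literally, that would put the last dose at Week 12 and the nominal Week 16 shortfall at 60 − 28 = 32 days.

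**What to change.** - **Section 6.4.1:** collect SAEs until the latest of end of participation, 30 days after withdrawal, and 60 days after the last dose of study drug.
- **Section 6.5:** write *study drug* for *benralizumab*, so that one rule applies under the blind.
- **Schedule:** add one telephone SAE contact at or after day 60 post-dose for subjects who skip OLE I or are withdrawn without withdrawing consent. Keep the Week 16 visit.
- **Section 9.4:** align the follow-up stop for known SAEs with the same date.

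As editorial tidying only, limit the Section 9.3 sentence to subjects who skip OLE I, match its ±3 days to the table's ±4, and change Visit 25 in the Section 4.5 text from Week 92 to the table's Week 96.

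The cost is a few sentences and one call per affected subject, with no new patients, clinic visits or endoscopies. Subjects who withdraw consent stay under Section 3.10.2, so the gap cannot be fully closed for them.

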9.4 Data management

Serious Adverse Event (SAE) Reconciliation

SAEs will be followed until they are resolved, with or without sequlae, or until the end of study participation, or until 30 days after the subject prematurely withdraws from the study (without withdrawing consent)/or is withdrawn from the study, whichever occurs first.

Data Management of genotype data

N/A

Data associated with human biological samples

N/A

Management of external data

N/A

10. ETHICAL AND REGULATORY REQUIREMENTS

10.1 Ethical conduct of the study

This study will be conducted using good clinical practice (GCP), as delineated in Guidance for Industry: E6 Good Clinical Practice Consolidated Guidance, and according to the criteria specified in this study protocol.

10.2 Subject data protection

Participant's privacy and confidentiality will be respected throughout the study. Each participant will be assigned a unique identification number and these numbers will be used to collect, store, and report participant information instead of the participant's name. Site personnel will not transmit documents containing personal health identifiers (PHI) to the study sponsor or their representatives.

10.3 Ethics and regulatory review

Before study initiation, the protocol and the informed consent documents will be reviewed and approved by the Cincinnati Children's Hospital Medical Center IRB (CCHMC IRB).

10.4 Informed consent

The Principal Investigator will designate appropriate study staff for performing the informed consent process.

During the consent process, study staff will provide information about the study to a prospective participant and will allow adequate time for review and discussion prior to his/her decision. The principal investigator or designee listed on the delegation log will review the consent and answer questions. The consent designee must be listed on the delegation log, have knowledge of the study and received training (from the local IRB, PI, or study coordinator) in the consent process. The prospective participant will be told that being in the trial is voluntary and that he or she may withdraw from the study at any time, for any reason. All participants (or their legally authorized representative) will read, sign, and date a consent form before undergoing any study procedures. Consent materials will be presented in participants' primary language. A copy of the signed consent form will be given to the participant.

This study will be conducted in compliance with ICH E6 GCP: Consolidated Guidelines pertaining to informed consent. At the first visit, prior to initiation of any study-related procedures, participants will give their written consent to participate in the study after having been informed about the nature and purpose of the study, participation/termination conditions, and risks and benefits. If the participant is unable to provide written informed consent, the participant's legally acceptable representative may provide written consent as approved by institutional specific guidelines. The informed consent document must be signed and dated by the participant, or the participant's legally authorized representative, prior to study participation. A copy of the informed consent document must be provided to the participant or the participant's legally authorized representative. Signed consent forms must remain in the participant's study file and be available for verification by the monitor, IRB, and/or regulatory authorities at any time. If participant's legally acceptable representative provides written consent, participants will also give their written assent to participate in the study as approved by institutional specific guidelines for obtaining assent.

The consent form will be revised when important new safety information is available, the protocol is amended, and/or new information becomes available that may affect participation in the study.

10.5 Changes to the protocol and informed consent form

Any amendments to the protocol or consent materials will be approved by the CCHMC IRB before they are implemented.

10.6 Audits and inspections

The study PI or CCHMC representative may subject this trial to quality assurance audits or inspections at any time. In the case of an audit or inspection, the investigator is responsible for the following:

- Informing the sponsor of a planned inspection by regulatory agencies as soon as they become aware of the inspection, and authorizing the sponsor to participate in the inspection
- Providing access to all necessary facilities, study data, and documents for the inspection or audit
- Immediately communicating any information arising from inspection by regulatory agencies to the sponsor
- Taking all appropriate measures requested by the sponsor to resolve any problems discovered during audit or inspection

Documents subject to audit or inspection include, but are not limited to:

- all source documents, CRFS, and ICFs
- medical records
- correspondence
- IRB/EC files
- documentation of certification and quality control of supporting laboratories
- records relevant to the study maintained in any supporting pharmacy facilities.

Study material storage data are also subject to inspection. Representatives of CCHMC may observe the conduct of any aspect of the trial or its supporting activities both within and outside of the investigator's institution.

In all instances, the confidentiality of the data must be respected.

LIST OF REFERENCES

3. Straumann A (2008) The natural history and complications of eosinophilic esophagitis. Gastrointest Endosc Clin N Am 18:99-118; ix. doi: 10.1016/j.giec.2007.09.009

Inclusion criteria "patient must be symptomatic" will be determined by the following assessment of symptoms and pain interference to a subject's daily life:

IRB# 2017-1701 Benralizumab Study Subject number:_____ Date of visit:

In the past 4 weeks, how have pain and symptoms affected your daily life? GI symptoms may include Nausea, pain, abdominal discomfort, diarrhea, heartburn, burping, constipation and others.

Ability to Participate in Social Roles and Activities	Never	1 time per week	2-3 times per week	4-5 times per week	6-7 times per week
How often did pain/symptoms interfere with					
your regular leisure activities with others, such					
as playing sports or participating in your					
hobbies?					
How often did pain/symptoms interfere with					
your day to day activities?					
How often did pain/symptoms interfere with					
your ability to go to work/ school and participate					
in classes, doing school work at home,					
chores/tasks you usually do around the					
home/place of work?					
How often did pain/symptoms interfere with					
your ability to participate in social activities,					
such as spending time with friends, attending					
events or parties, or going on dates?					
How many times have your symptoms					
interfered with your daily life in any way?					

For inclusion: At least 1 question must be answered with 2-3 time per week and up.

OR,

At least 2 questions must be answered with 1 time per week and up.

Inclusion criteria Pass/Fail (circle)

PI signature:	Date:
